## SUMMARY OF CHANGES

Version	Location of Change	Description of Change
3.0	Global	Minor formatting, typographical, and grammatical errors were corrected.
3.0	Sponsor Signature Page	The Sponsor signatory was changed from [REDACTED] to [REDACTED].
3.0	Medical Contact/Sponsor Information Page	The secondary medical monitor was changed from [REDACTED] to [REDACTED].
3.0	Table of Contents; List of Tables, List of Figures	Fields were updated.
3.0	1	The approximate number of study sites was updated.
3.0	1; 5.1.1	Reference to electronic completion of questionnaires was removed.
3.0	1; 3; 9.2.1	A clarification was added that primary safety will assess adverse events that are treatment-emergent.
3.0	1; 3	The endpoint categories of “Secondary Efficacy” and “Exploratory Efficacy” were renamed to “Secondary” and “Exploratory”, respectively.
3.0	1; 3; 9.3.1	The following endpoints previously included as “Secondary Efficacy” endpoints were moved to “Exploratory” endpoints. 

3.0	1	The statistical methods section was reordered with the sample size information appearing first.

Version	Location of Change	Description of Change
3.0	1; 9.3; 9.4.1; 9.4.2; 9.5; 9.5.1; 9.6; former 9.8 (removed)	The description of statistical methods was revised in accordance with statistical analysis only being performed for the following 4 secondary endpoints: 
 
• Change from baseline (CFB) at Week 52 in average number of micturitions per 24 hours in all OAB patients;
 
• CFB at Week 52 in average number of urge urinary incontinence (UUI) episodes per 24 hours in OAB Wet patients;
 
• CFB at Week 52 in average number of urgency episodes (need to urinate immediately) over 24 hours in all OAB patients;
 
• CFB at Week 52 in average number of total urinary incontinence episodes over 24 hours in OAB Wet patients.
 
 All analysis will be considered descriptive only.
3.0	1.1	A Week 12 physical exam was included in the Schedule of Activities.
3.0	1.1; 8.3.1	Text was updated to indicate the collection period for adverse events and serious adverse events will begin following the first dose of Study Treatment in RVT-901-3004.
3.0	1.1; 8.3.1	Phrasing was removed that limits the collection of adverse events to events “deemed related to study procedures” (all adverse events are recorded).
3.0	4.1	The paragraphs in the study design section were reorganized to match the order in the synopsis.
3.0	6.4; 9.1	Text on blinding was updated to reflect an updated blinding strategy for the study as double-blind, Sponsor open (partially unblinded).
3.0	7.7.1	A clarification was added that all prior OAB meds should be assessed during prior medications review.
3.0	7.7.3	A clarification was added that prohibition of medications with a narrow therapeutic index is specific only to the example drugs provided.
3.0	7.8; 9.3.1	A clarification was added for the definition of “Complete Diary Day”.
3.0	8.3.3	A clarification was added that overdose events that do not result in an adverse event will be reported as a protocol deviation in the eCRF.
3.0	1; 9.4	“Extension” was added to analysis population names to distinguish analysis sets from this study versus RVT-901-3003.
2.0	Cover page	Added Basel address; changed study director contact.
2.0	Global	Minor typographical/grammatical errors were corrected.

Version	Location of Change	Description of Change
2.0	Medical Contact/Sponsor Information Page	Update [REDACTED] to [REDACTED] and [REDACTED] to [REDACTED] to reflect new companies.
2.0	Table of Contents	Updated all page numbers; Sections 5.4 and 5.4.1: Replaced “Discontinuation” with “Interruption” and removed “Withdrawal from the Study”.
2.0	1; 3; 9.3.1	Addition of two exploratory efficacy endpoints [REDACTED]
2.0	1; 2.1	Addition of (RVT-901) after Vibegron to align with Certificate of Analysis for product.
2.0	1; 3; 9.2.2; 9.3.1; 9.5.1	[REDACTED]
2.0	1.1	Updated Schedule of Activities and visit events to reflect protocol text; updated and realigned footnotes accordingly.
2.0	5.4; 5.4.1	Replaced “discontinuation” with “interruption”; reversed order of sentences.
2.0	6.6	Removed study medication rechallenge in patients with a grade 3 or higher drug-related AE reported.
2.0	7	Moved Visit Reminders to 7.10.
2.0	7.8; 7.8.1	Updates to Patient Voiding Diary instructions, training, and description.
2.0	7.9; 7.9.1; 7.9.2	Updates to Urine Volume Collection instructions, training, and description.
2.0	7.10	Update to instructions on Reminders for Diary Collection.
2.0	7.11; 7.11.1; 7.11.2	Updates to Electronic Diary instructions and training.
2.0	8.3.1	Updated and condensed section wording for Reporting Adverse Events.
2.0	8.6	Updated MACCE language to match CAC Charter.
2.0	8.7	Addition of timeframe around pregnancy and infant outcome.
1.1	Global	Minor typographical/grammatical errors were corrected.
1.1	Sponsor Signature Page	Minor wording update to sentence: This protocol has been approved by a representative of Urovant Sciences GmbH.
1.1	1	Wording in study design description changed from “at approximately 100 study sites” corrected to “at approximately 330 study sites.”

Version	Location of Change	Description of Change
1.1	1; 5.1.1	Inclusion criterion #3 updated to reflect wording in Section 5.2.1.
1.1	1.1	Footnotes were updated to include: a note that paper diaries may be used with timing for their collection included; clarification that urinalysis will be performed if there is a positive dipstick result.
1.1	1.1	eDiary completion for the Week 44 Visit was added.
1.1	5.2.1	Changes were made to description of contraception requirements and methods for female patients
1.1	6.1	“Tablet” or “capsule” descriptors were added to Table 6-1.
1.1	6.2	Wording was added to indicate the study treatment should be swallowed whole.
1.1	7.2; 7.16	Clarified that tablet/capsule count will be recorded in the interactive voice or web response system rather than case report form.
1.1	7.4	The timing for collection of paper diaries (if used) was added.
1.1	7.4.4	Removed reference to pharmacokinetic sampling as this is not performed in this extension study.
1.1	8.6	Added adverse events suggestive of cystitis or urinary tract infection and moved liver test values to end of list.

### Study Sponsor:

This study is sponsored by Urovant Sciences GmbH.

## 1. SYNOPSIS

Study Title	An International Phase 3, Randomized, Double-Blind, Active (Tolterodine)-Controlled Multicenter Extension Study to Evaluate the Long-Term Safety and Efficacy of Vibegron in Patients with Symptoms of Overactive Bladder
Protocol Number	RVT-901-3004
Study Center Location(s)	International
Number of Study Centers Planned	~110
Study Phase	3
Target Population	Adult men and women with either: 
 
• Overactive bladder (OAB) Wet; or
 
• OAB Dry
 

Number of Patients Planned	500
Study Objectives	
Primary Safety Objective	
 
• To evaluate the safety and tolerability of vibegron (RVT-901) for up to 52 weeks in patients with symptoms of overactive bladder (OAB) who previously completed treatment in study RVT-901-3003
 

Secondary and Exploratory Objectives	
 
• To evaluate the efficacy of vibegron in patients with symptoms of OAB
 

Study Design	
This is an international Phase 3, double-blind, active (tolterodine)-controlled, parallel-group, multicenter, 40-week extension study to evaluate the safety, tolerability, and efficacy of vibegron 75 mg in men and women with symptoms of overactive bladder syndrome (OAB). This study is an extension for patients who have completed the Phase 3, double-blind, randomized, 12-week study RVT-901-3003.
 
Approximately 500 men and women with overactive bladder who completed 12 weeks in study RVT-901-3003 will be permitted to enroll in this extension study, at approximately 110 study sites.
 
During this extension study, all patients who had been randomized in RVT-901-3003 to receive either vibegron 75 mg or tolterodine ER 4 mg will continue their same treatment once daily in a blinded fashion for an additional 40 weeks; patients who had been randomized in RVT-901-3003 to the placebo group will be randomized 1:1 to receive blinded study treatment of vibegron 75 mg or tolterodine ER 4 mg once daily for 40 weeks during the extension. Thus, through participation in both the RVT-901-3003 study and the RVT-901-3004 (extension) study, patients originally randomized to vibegron or tolterodine will receive 52 weeks total of vibegron or tolterodine treatment, and patients originally randomized to placebo will receive 40 weeks total of vibegron or tolterodine treatment.

	
Study visits will be named to reflect continuation from the RVT-901-3003 study, with the first study visit of this extension study occurring at Study Treatment Week 12. Following enrollment in this extension study, patients will return to the clinic for visits at Week 16, Week 24, Week 36, Week 44, and Week 52 (all relative to Day 1 of RVT-901-3003). The Schedule of Activities (Section 1.1) summarizes the assessments/procedures to be performed at each visit.
 
This study consists of a randomized double-blind Treatment Period (40 weeks), and a Safety Follow-up Period (4 weeks). All patients will have a Follow-up Visit approximately 28 days after the patient’s last dose of study treatment (i.e., at Week 56 for patients who complete the Week 52 Visit, or approximately 4 weeks after withdrawal for patients who discontinue the study early). Additionally, unscheduled follow-up visit(s) may be arranged for patients with study-related safety concerns as needed.

Study Treatments
	
The investigator, site staff, and the patients will remain blinded to the Study Treatment during this extension study.
 
All treatments are dosed orally, once daily (QD). Patients will receive one of the following blinded treatments:
 
 
• Vibegron 75 mg tablet + placebo capsule to match tolterodine ER 4 mg capsule (N = 267)
 
• Tolterodine ER 4 mg capsule + placebo tablet to match vibegron 75 mg tablet (N = 233)
 
 
All patients previously randomized to placebo in RVT-901-3003 will be randomized 1:1 to receive vibegron 75 mg tablet + placebo capsule to match tolterodine ER 4 mg capsule or tolterodine ER 4 mg capsule + placebo tablet to match vibegron 75 mg tablet, in this extension study.

Duration of Treatment
	
40 weeks
 
Note: upon entering this extension study, all patients will have already received 2 weeks of treatment with placebo plus an additional 12 weeks of treatment with vibegron, tolterodine, or placebo in the RVT-901-3003 study.


Eligibility Criteria Inclusion Criteria
	
 
1. Has completed participation in study RVT-901-3003.
 
2. Willing and able to provide written informed consent.
 
3. For females of reproductive potential: Agrees to remain abstinent or use (or have their male partner use) an acceptable method of birth control (as defined in Section 5.2.1) each time the patient has intercourse until the Follow-up Visit.
 
4. For females of reproductive potential: Agrees not to donate ova (eggs) until at least 1 month after the last dose of Study Treatment.
 
5. Has demonstrated <math>\geq 80\%</math> compliance with self-administration of Study Treatment in study RVT-901-3003.
 
6. Has completed a minimum of 4 Complete Diary Days for study RVT-901-3003 Week 12.
 

	
 
7. Is ambulatory and in good general physical and mental health as determined by the Investigator.
 
8. In the opinion of the Investigator, is able and willing to comply with the requirements of the protocol, including completing questionnaires, the Voiding Diary, and Voided Volume Diary (will require ability to collect, measure, and record voided volume by herself/himself using a graduated urine collection and measurement container [provided by the Sponsor, if needed]).
 


Exclusion Criteria
	
 
1. Was unable to complete participation in study RVT-901-3003 for any reason.
 
2. Has a change in history or current evidence of any clinically significant condition, therapy, lab abnormality, or other circumstance that might, in the opinion of the Investigator, confound the results of the study, interfere with the patient's ability to comply with study procedures, or make participation in the study not in the patient's best interest. Includes any serious or unstable, clinically relevant change in gastrointestinal, renal, hepatic, cardiovascular, lymphatic, or psychiatric, or other medical disorder during the RVT-901-3003 study
 
3. Has coronary or neurovascular interventions planned during the duration of the study.
 
4. Has uncontrolled hyperglycemia (defined as fasting blood glucose >150 mg/dL or 8.33 mmol/L and/or non-fasting blood glucose >200 mg/dL or 11.1 mmol/L) based on most recent available lab results in study RVT-901-3003 or, if in the opinion of the Investigator, is uncontrolled.
 
5. Has uncontrolled hypertension (systolic blood pressure of <math>\geq 180</math> mm Hg and/or diastolic blood pressure of <math>\geq 100</math> mm Hg) or has a resting heart rate (by pulse) > 100 beats per minute.             
 
a. Patients who have systolic blood pressures <math>\geq 160</math> mm Hg or < 180 mm Hg are excluded, unless deemed by the Investigator and/or Medical Monitor as safe to proceed in this study and able to complete the study per protocol; these patients must be on stable hypertension medication for at least 90 days.
 
b. All patients with signs and symptoms of uncontrolled hypertension, regardless of blood pressure measurement, are excluded from the study. These include, but are not limited to neurological symptoms or findings, hematuria, proteinuria, retinopathy, unstable angina, acute heart failure.
 
 
 
6. Has clinically significant ECG abnormality which, in the opinion of the Investigator, exposes the patient to risk by participating in the study
 
7. Has alanine aminotransferase or aspartate aminotransferase > 2.0 times the upper limit of normal (ULN), or bilirubin (total bilirubin) > 1.5 x ULN (or > 2.0 x ULN if secondary to Gilbert syndrome or pattern consistent with
 

	
Gilbert syndrome) based on most recent available lab results in study RVT-901-3003.
 
 
8. Has an estimated glomerular filtration rate (eGFR) < 30mL/min/1.73 m^2 based on most recent available lab results in study RVT-901-3003.
 
9. Use of any prohibited medications as detailed in Section 7.7.3.
 
10. Plans to initiate or change the dosing of any medications listed in Section 7.7.5 during the study that in the opinion of the investigator is assessed to be clinically significant.
 
11. Has an allergy, intolerance, or a history of a significant clinical or laboratory adverse experience associated with any of the active or inactive components of the vibegron formulation or tolterodine formulation.
 
12. Is currently participating or has participated in a study with an investigational compound or device within 28 days of signing informed consent, not including participation in study RVT-901-3003.
 
13. Has a history of significant drug or alcohol abuse/dependence within a year of informed consent, as assessed by the investigator.
 
14. Has a varying sleep schedule anticipated during times when the voiding diaries are to be completed.
 

Endpoints	
Primary Safety	
 
• Incidence of any treatment-emergent adverse event by system organ class and preferred term
 

Secondary Endpoints	
 
• Change from baseline (CFB) at Week 52 in average number of micturitions per 24 hours in all OAB patients
 
• CFB at Week 52 in average number of urge urinary incontinence (UUI) episodes per 24 hours in OAB Wet patients
 
• CFB at Week 52 in average number of urgency episodes (need to urinate immediately) over 24 hours in all OAB patients
 
• CFB at Week 52 in average number of total urinary incontinence episodes over 24 hours in OAB Wet patients
 

Exploratory Endpoints	

Statistical Methods	
Sample Size Estimation	Five hundred (500) patients rolling over from study RVT-901-3003, in addition to other long-term safety data with vibegron, is sufficient to characterize the long-term safety profile of vibegron 75 mg once daily and satisfies the International Conference on Harmonisation of Technical Requirements for Registration of Pharmaceuticals for Human Use (ICH) guidance for 1-year exposure.
Safety	
Safety assessments will include treatment-emergent adverse events, clinical laboratory tests, physical examinations, vital signs, and 12-lead ECGs. Safety analyses will be based on all patients who receive any amount of blinded study drug (through Week 52 of this extension study). Two treatment groups will be used for reporting of safety data and will be determined based on randomized treatment in RVT-901-3004. Baseline will be the RVT-901-3003 baseline.
 
Descriptive statistics will be used to summarize safety endpoints. No formal statistical comparisons will be performed.

Efficacy	
The efficacy analyses will be for descriptive purposes only and will be conducted using the FAS-Extension population, which is a subset of the RVT-901-3003 treated population who have completed the 12-week treatment period in RVT-901-3003 and enrolled into this extension study.
 
The efficacy endpoints of change from baseline in average number of micturitions, average number of UUI episodes, average number of urgency episodes, and average number of total incontinence episodes will be analyzed separately using a mixed model for repeated measure (MMRM) with restricted maximum likelihood estimation. The analysis model for each efficacy endpoint will include terms for treatment, visit, baseline stratification factors (those found to be significant in RVT-901-3003), baseline score, and interaction of visit by treatment. An unstructured covariance matrix will be used to model the correlation among repeated measurements. The Kenward-Roger adjustment will be used with restricted (or residual) maximum likelihood (REML) to make statistical inference. Adjusted means for each treatment group and visit will be estimated along with 95% confidence intervals. No formal statistical comparisons will be made. Only the 52-week subjects (those on active treatment in RVT-901-3003 and in RVT-901-3004) will be included in the model.
 
Descriptive statistics will be used to summarize all efficacy endpoints. Summaries of efficacy endpoints will be presented by treatment group where the 4 treatment groups will be determined by randomized treatment in both RVT-901-3003 and RVT-901-3004. Baseline will be the RVT-901-3003 baseline.

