#### 9.2.1. Primary Objective and Hypotheses

The primary objective will be to demonstrate the long-term safety of vibegron 75 mg in patients with symptoms of OAB. There is no formal statistical primary endpoint hypothesis. Rather, incidence of treatment-emergent AEs by system organ class and preferred term will be descriptively summarized by treatment group based on study RVT-901-3004.

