## **9.4. Analysis Populations**

### **9.4.1. Efficacy Analysis Populations**

The Full Analysis Set Extension (FAS-Ext) population will serve as the population for the analysis of efficacy data in this study. Since the endpoints related to incontinence would only apply to patients who meet the definition of incontinence at study entry, it is necessary to have a separate FAS definition with an additional criterion to define the analysis population for incontinence endpoints.

The following FAS populations are defined in the study:

- Full analysis set extension (FAS-Ext): all OAB patients who took at least one dose of double-blind Study Treatment in the current study and have at least one evaluable change from baseline micturition measurement in this study
- Full analysis set extension for incontinence (FAS-Ext-I): all OAB Wet patients who took at least one dose of double-blind Study Treatment in the current study and have at least one evaluable change from baseline urge urinary incontinence measurement in this study

The Per-Protocol extension population (PP-Ext) and Per-Protocol extension population for incontinence (PP-Ext-I) exclude patients due to important deviations from the protocol that may substantially affect the results of the efficacy endpoints. A supportive analysis using the Per-

Protocol populations will be performed for the 4 key secondary efficacy endpoints. The final determination on protocol violations, and thereby the composition of the Per-Protocol population, will be made prior to the unblinding of the database and will be documented in a separate memo.

Patients will be included in the treatment group to which they are randomized to for the analysis of efficacy data using the Full Analysis Set and Per-Protocol populations. Efficacy endpoints will be descriptively summarized by treatment group based on treatment in both RVT-901-3003 and study RVT-901-3004. This means there will be 4 treatment groups including vibegron for 52 weeks, tolterodine for 52 weeks, vibegron for 40 weeks, and tolterodine for 40 weeks.

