#### **9.4.2. Safety Analysis Populations**

The Safety Analysis (SAF) population will be used for the analysis of safety data in this study. The SAF population consists of all patients who received at least one dose of Study Treatment in this study. Patients will be included in the treatment group corresponding to the Study Treatment they actually received for the analysis of safety data using the SAF population. For most patients, this will be the treatment group to which they were randomized. Patients who take incorrect Study Treatment for the entire Treatment Period will be included in the treatment group corresponding to the Study Treatment actually received. Safety endpoints will be descriptively summarized based on treatment in study RVT-901-3004. This means there will be 2 treatment groups including vibegron (52 weeks and 40 weeks combined) and tolterodine (52 weeks and 40 weeks combined).

At least one laboratory or vital sign measurement obtained subsequent to at least one dose of Study Treatment is required for inclusion in the analysis of each specific parameter. To assess change from baseline, a Baseline measurement is also required.

No imputation will be performed for missing safety data. Baseline will be defined as the last non-missing value before double-blind treatment in study RVT-901-3003. Further inclusion of data from RVT-901-3003 in the reporting of this study will be described in the SAP.

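### The primary adverse-event tables pool new starters and continuing patients in one column per drug, so one incidence mixes drug weeks 0–40 with drug weeks 12–52 and describes neither group

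*Protocol*

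**What the plan says.** The primary endpoint is the incidence of treatment-emergent adverse events (TEAEs) by system organ class and preferred term. Three places set how it is grouped:

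- Synopsis, Statistical Methods, Safety: "Two treatment groups will be used for reporting of safety data and will be determined based on randomized treatment in RVT-901-3004".
- Section 9.2.1: "incidence of treatment-emergent AEs by system organ class and preferred term will be descriptively summarized by treatment group based on study RVT-901-3004".
- Section 9.4.2: "2 treatment groups including vibegron (52 weeks and 40 weeks combined) and tolterodine (52 weeks and 40 weeks combined".

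Efficacy is handled differently. Section 9.4.1 summarises it in "4 treatment groups including vibegron for 52 weeks, tolterodine for 52 weeks, vibegron for 40 weeks, and tolterodine for 40 weeks", and the efficacy model in Section 9.5.1 admits only patients who were on active treatment in both studies.

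Section 6.3 sets the allocation. Former vibegron and tolterodine patients keep their drug. Only former placebo patients are newly allocated by chance; in the synopsis, "All patients previously randomized to placebo in RVT-901-3003 will be randomized 1:1" to the two drugs. The synopsis plans 267 patients on vibegron and 233 on tolterodine.

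Under Section 9.5.2 the treatment-emergent period starts at the first dose in this study. Section 8.3.1 assigns earlier events to RVT-901-3003.

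**The concern.** Each safety column holds two kinds of patient. Former placebo patients start active drug at Week 12 and are followed from their first active dose. Continuing patients enter after 12 weeks on the same drug, and whatever happened in those weeks is counted in the other study. For an event that tends to appear early, the two groups have different expected incidences in this study for reasons of timing and prior tolerance alone.

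At stake is how the primary result can be read. A pooled figure understates what a patient starting the drug experiences and overstates what an established patient experiences. The objective concerns safety for up to 52 weeks, yet the vibegron patients who can reach 52 weeks are not shown apart from those who can reach only 40. Nor are the two groups that randomisation in this study makes comparable.

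**Working it through.** **Inputs from the protocol.** Planned arms are 267 and 233 (synopsis), and 267 + 233 = 500 matches the planned total. Former placebo patients split 1:1 (Section 6.3). The window runs from the first dose in this study to 28 days after the last (Section 9.5.2).

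**Input not given.** Neither the number of former placebo patients nor the parent allocation ratio is stated. Let V, T and P be the former vibegron, tolterodine and placebo patients, and s = P/2 the new starters per arm. Then V + s = 267 and T + s = 233, so V − T = 34 whatever P is. I assume s = 50 to 100. If former vibegron and placebo patients enter in equal numbers (V = P), then 1.5P = 267, so P = 178, s = 89 and T = 144; 178 + 178 + 144 = 500.

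**Observation time on drug.**

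| Group | Allocated by chance in this study | Drug weeks observed on treatment |
|---|---|---|
| 40-week vibegron and tolterodine | Yes, 1:1 | 0–40 |
| 52-week vibegron and tolterodine | No, carried over | 12–52 |

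**Formulas.** Share of new starters = s/267 (vibegron) or s/233 (tolterodine). Pooled incidence = continuing rate + share × (new-starter rate − continuing rate). The rates are assumed, and identical for both drugs, so any gap between arms comes only from the mix. Each cell gives vibegron / tolterodine.

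| s per arm | Share of new starters | Event at 8% new, 2% continuing | Any TEAE at 60% new, 45% continuing |
|---|---|---|---|
| 50 | 18.7% / 21.5% | 3.12% / 3.29% | 47.8% / 48.2% |
| 89 | 33.3% / 38.2% | 4.00% / 4.29% | 50.0% / 50.7% |
| 100 | 37.5% / 42.9% | 4.25% / 4.58% | 50.6% / 51.4% |

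For example, 2 + (50/267) × 6 = 3.12.

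**Dilution within a column.** Against the 8% new-starter rate, the pooled figure is 3.12/8 = 39% to 4.58/8 = 57%. Against the 2% continuing rate it is 3.12/2 = 1.6 to 4.58/2 = 2.3 times too high.

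**Effect between columns.** At the planned sizes the shares stand in the ratio 267/233 = 1.146. The resulting gap is 0.2 to 0.3 points in the 8%/2% example and 0.4 to 0.8 points in the 60%/45% example. A wider assumed contrast of 60% against 30% with s = 89 gives 40.0% and 41.5%, a gap of 1.5 points. For comparison, the 95% half-width for a difference between 267 and 233 patients is about ±3.6 points at 4.25% against 4.58%, and about ±8.8 points near 50%.

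**Precision of separate columns.** The 95% half-width at 8% incidence is 1.96 × √(0.08 × 0.92/n), which is 7.5 points for n = 50 and 5.3 for n = 100.

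**The case against.** The pooling is stated openly and consistently, so it is a choice and not a contradiction. Safety is descriptive: there is no safety hypothesis and no formal comparison of the drugs, so no error rate or power is affected. The aim is long-term safety, and the 12-week parent study already gives a randomised comparison of vibegron, tolterodine and placebo from the first dose. Section 9 calls itself a brief summary and leaves full details to the SAP, which could add tables by prior treatment. Prior treatment and event dates are recorded, so the split can be tabulated later with nothing lost. All of this stands, and it makes the point one of presentation.

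Some stronger readings are tempting but unsupported:

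- A reader might infer that former placebo patients will never be shown separately. Efficacy already separates them, and the SAP may do so for safety.
- A reader might infer that the arms are distorted by a fixed ratio in favour of vibegron. The 1.146 holds only if enrolment lands on 267 and 233; Section 6.3 caps the total and not the arms, and equal numbers of former vibegron and tolterodine patients would bring the ratio to about 1. The direction reverses for events commoner in longer-exposed patients.
- A reader might infer that the 80% compliance rule selects only the continuing patients. Section 5.1.1 applies it to every entrant; what differs is having completed 12 weeks on the active drug.

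The deferral to the SAP does not remove the core. The protocol does not leave the grouping of the primary endpoint open: it fixes the two combined columns. What Section 9.4.2 defers is further use of RVT-901-3003 data.

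**Conclusion.** The concern holds as a point about how the primary safety result is displayed. Two pooled columns, with a window that opens at the first dose in this study, mix two different stretches of drug exposure. On the assumed 8% and 2% rates with 50 to 100 new starters per arm, the column reads about 3% to 5%, or roughly 40% to 57% of the new-starter rate. These rates and patient numbers are assumptions. That the columns mix the two exposure periods follows from the protocol's own text.

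The difference in new-starter shares between arms is secondary: under 1 point on the main assumed rates, and 1.5 points in the wider example. Both are well inside sampling error. The documents do not support calling the safety comparison biased in a known direction, or saying that the plan invalidates the primary analysis. This is a cheap improvement worth making.

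**What to change.** In the synopsis (Statistical Methods, Safety) and Sections 9.2.1 and 9.4.2, state that any TEAE, TEAEs by system organ class and preferred term, and adverse events leading to discontinuation will be shown in the four treatment-history columns already defined in Section 9.4.1, with the two pooled columns kept beside them. Add a note that the two 40-week columns are the groups formed by randomisation in this study, and that the 52-week columns cover events from Week 12 only.

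The cost is a change of wording and extra columns in existing tables; no new data, visits or patients are needed. The drawback is precision: with 50 to 100 patients, each 40-week column carries about ±5 to ±8 points at 8% incidence. The pooled columns therefore remain useful, especially for rare events. The split does not bring the first 12 weeks of continuing patients into view; that depends on the parent-study data, whose use the protocol leaves to the SAP.
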